FACULTY ETHICS SUB GROUP APPLICATION FORM

efficacy will also be explored as the systematic review demonstrated that symptom monitoring is related to improved efficacy in making medical decisions. This evidence also suggested that symptom monitoring may improve an individual's ability to identify which health improvements they would like to see in the future, therefore goal-setting efficacy will be assessed. Lastly, health awareness will be explored following evidence from the systematic review which suggested that symptom monitoring increased awareness of symptoms, which was subsequently associated with symptom improvements (Stensland & Malterud, 2001).

A secondary objective is to explore the potential moderators of the impact of symptom monitoring on physical or emotional symptoms. For example, the dispositional characteristic neuroticism has been shown in numerous studies to lead to reports of more frequent and/or severe symptoms (Ormel, Rosmalen, & Farmer, 2004; Lagoe & Atkin, 2015). Trait neuroticism is important to explore in this research as it has empirically been associated with increased reports of health anxiety. Increasing evidence suggests that the relationship between trait neuroticism and health anxiety is mediated by health information seeking (Lagoe & Atkin, 2015). Therefore, it's important to assess whether health information, as supplied by symptom monitoring, could instigate heightened health anxiety in individuals with high neuroticism scores. Moreover, neuroticism has been related to increased reports of physical symptoms in terms of both severity and frequency, even when comparing objectively healthy populations (Pennebaker, 2012). This suggests that individuals scoring high on trait neuroticism may tend to report an increased number of symptoms, and this effect will be important to explore in regard to evaluating the symptom monitoring intervention.

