Monitoring and blunting coping tendencies have also been shown to influence the extent to which individuals prefer to pay close attention to their wellbeing or avoid thinking about it (Murris & Van Zuuren, 1992; Miller, 1987). Those who employ monitoring to cope with health problems will actively seek out health information, whereas those who employ blunting will adopt distraction strategies in order to actively avoid health information (Miller, 1995). This information seeking preference is important as evidence suggests that acquisition of health information can lead to increased health anxiety in individuals who exhibit monitoring coping preferences (Miller, 1995). In the case of menopausal symptom monitoring, women's attention is drawn to information about their menopausal wellbeing, which may be anxiety provoking. Therefore, this measure will help us understand whether symptom monitoring is more or less effective as an intervention for women, depending on their health information-seeking preferences.

It is important to establish for whom symptom monitoring might be most helpful, or conversely taxing or even harmful should it challenge a dispositional tendency to avoid focusing on wellbeing. Indeed, coping style and neuroticism have both been associated with increased health anxiety following the procurement of health information (Lagoe & Atkin, 2015; Miller, 1987). Therefore, health anxiety will also be measured during this research to explore whether symptom monitoring influences it, and whether this effect is related to neuroticism or coping preferences.

A third objective is to investigate whether participants attribute the act of monitoring to any perceived improvements, or whether participants attribute other elements of research participation to their improved health (i.e. increased menopausal awareness), or whether participants do not perceive any improvements whatsoever. Studies which have included symptom monitoring as a control intervention often speculate that involvement in research is responsible for the positive outcomes found in the control group, rather than symptom monitoring in itself (Borud et al., 2010). However, these studies rarely provide data on this assumption. Therefore, the present study aims to establish whether participation in menopausal research per se improves wellbeing, regardless of what that participation entails.

Summary of objectives:

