- Investigate whether daily symptom monitoring influences psychological, physical and behavioural health outcomes compared to a non-monitoring control group.
- Assess whether personality and coping style moderate the impact of symptom monitoring on physical or emotional health outcomes during the menopause.

[figure not shown]
FACULTY OF LIFE SCIENCES AND EDUCATION
FACULTY ETHICS SUB GROUP APPLICATION FORM

- Identify whether participants attribute any health improvements to symptom monitoring, or other elements of their research participation.

8. STATEMENT OF STUDY DESIGN (E.g. RCT, Crossover, Cohort studies, Case control, Action research, etc. Max 700 words)

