interested in receiving text message reminders, participants in the control group will also be sent a reminder text message to complete the follow-up survey.

Hypotheses:

- Symptom monitoring will lead to significant improvements in symptoms after 2 weeks, in comparison to the non-monitoring control group.
- The monitoring group will report increased self-efficacy at follow up in patient-doctor communication, shared decision making, goal orientated behaviour, help-seeking intentions, and heightened health awareness, compared to the control group.
- Women in the intervention group who are monitors according to their scores on the blunting and monitoring scale will report higher negative emotions and physical symptoms than blunters at follow up.
- Greater Health anxiety at follow up will be predicted by symptom changes, demographics (living alone, employment, and marital status), coping style, neuroticism, and symptom monitoring.

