Demographics and medical history (baseline only): Demographic variables to be measured are: age, town/country of residence, menopausal status, employment status, relationship status, living arrangements (i.e. are they living alone or with others?), date of last menstrual period, current medications being used (both for menopause and other conditions), and any current medical conditions. **See Appendix 1, page 2 to view how the demographic and medical history questions will be presented on the baseline survey.**

Blunting and monitoring coping preferences as measured using the Miller Behavioural Style Scale (MBSS; at baseline only): this will be used to assess dispositional monitor/blunter coping preferences, which might affect the extent to which women benefit from or feel uncomfortable with symptom monitoring. The MBSS asks the recipient to vividly imagine 4 different scenarios, and then choose how they would respond to each one from a list of statements. These statements give an indication of whether the respondent would react to the imagined situation by using a Monitoring or Blunting coping strategy. Three scores can be derived from the MBSS questionnaire. They are: (1) the total Monitoring score; (2) the total Blunting score; or (3) the total difference score- Monitoring minus Blunting. To create the total Monitoring and Blunting scores simply sum the Monitoring items (marked "M") and the number of Blunting items (marked "B") respectively. Once these individual scale scores are created, you can simply put them into the M-B equation to create the total difference score. **See Appendix 10, page 1 to view a copy of the original MBSS, see Appendix 1, page 13 to view how the MBSS will be presented on the baseline survey.**

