Health anxiety subscale extracted from The Health Orientation Scale, $\alpha = .82$ (HOS; to be assessed at baseline and follow-up): health anxiety will be assessed to explore whether symptom monitoring influences it, and whether this effect is related to neuroticism or coping preferences. The HOS was developed by William E. Snell, and includes 10 health-oriented subscales each containing five items. The items on the health anxiety subscale assesses anxious feelings associated with the status of one's health. More specifically, these items were designed to tap people's feelings of tension, discomfort and anxiety about their physical health. People who endorse these items are those who experience chronic anxiety as a result of thinking about their physical health (Snell et al., 1991). The 5-item health anxiety subscale has good reliability, and has been used in numerous studies as a measure of health anxiety (Adejumo et al., 2017; Gordon et al., 2005; Snebby & Snell, 2002). **See Appendix 10, page 4 to view a copy of the original HOS including the Health Anxiety subscale, see Appendix 1, page 5 to view how the Health Anxiety subscale will be presented on the baseline survey. See Appendix 3, page 2 to see how to Health Anxiety subscale will be presented on the follow-up survey. On the baseline and follow-up surveys the health anxiety subscale is presented together with the health consciousness subscale and titled "Thoughts about health questionnaire".**

Patient-doctor communication will be assessed using the Willingness to Communicate about Health (WTCH) Measure, $\alpha = .70$: this variable will be explored following evidence from the systematic review which suggested that willingness to communicate about one's health might increase following symptom monitoring. This was because individuals felt better able to describe the totality of their symptoms after summarising them using a symptom monitoring instrument (Ismail et al., 2016; Woods et al., 2015).

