22. DATA ANALYSIS / STATISTICS

Please describe the arrangements for analysing your data (qualitative and quantitative). Where appropriate discuss what data/statistical analysis will be completed. Where used, please remember to discuss sample size and how the sample size was decided upon.

2 x 2 mixed between-within ANOVA:

The main analysis will include a 2x2 mixed between-within ANOVA to assess differences in symptoms among the symptom monitoring and control groups before and after the 2-week research period. The between-subjects component will encompass the differences in symptoms between the control and intervention groups; the within-subjects variable refers to differences in symptoms before and after the 2-week study period. It is expected that after 2 weeks of symptom monitoring the intervention group will exhibit a greater reduction in symptoms in comparison to the control group (i.e., a significant group x time interaction). As discussed, a power analysis was calculated to identify the minimum sample size needed to detect moderate effects, resulting in the decision to recruit 78 participants, with 39 participants being randomised into each group.

Regressions:

Multiple regressions will explore whether help-seeking intentions as continuous variables as predicted by symptom monitoring group (dummy coded), self-efficacy in patient-doctor communication, self-efficacy in shared decision making, health and symptom awareness, and self-efficacy in goal orientated behaviour, health anxiety, and menopausal symptom changes.

Logistic regressions will establish whether control or intervention group membership (as measured as a dichotomous “Invention/Control” variable) is predicted by health anxiety, variances in emotions and symptoms, help-seeking intentions, self-efficacy in patient-doctor communication, self-efficacy in shared decision making, health and symptom awareness, and self-efficacy in goal orientated behaviour.

Correlations:

FACULTY OF LIFE SCIENCES AND EDUCATION
FACULTY ETHICS SUB GROUP APPLICATION FORM

Correlations will also be computed to assess for associations between certain variables. For example, higher neuroticism X higher negative emotions.

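### The plan sets out to test whether coping style and neuroticism moderate the effect of monitoring, but no planned analysis contains an arm-by-trait interaction

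*Combined protocol and SAP*

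**What the plan says.** The summary of objectives in Section 7 includes: "Assess whether personality and coping style moderate the impact of symptom monitoring on physical or emotional health outcomes during the menopause". The same section says the coping measure will show "whether symptom monitoring is more or less effective as an intervention for women, depending on their health information-seeking preferences", and adds that it matters to know for whom monitoring helps or harms. Section 9 asks the same of health anxiety: "health anxiety will be assessed to explore whether symptom monitoring influences it, and whether this effect is related to neuroticism or coping preferences".

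The analyses offered against this are:

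- **Section 8, hypothesis 3:** "Women in the intervention group who are monitors according to their scores on the blunting and monitoring scale will report higher negative emotions" and more physical symptoms than blunters at follow-up.
- **Section 8, hypothesis 4:** health anxiety at follow-up is predicted by symptom changes, "demographics (living alone, employment, and marital status), coping style, neuroticism, and symptom monitoring".
- **Section 22:** a 2x2 mixed ANOVA whose interaction is group by time; multiple regressions for help-seeking intentions; logistic regressions for group membership; and correlations: "Correlations will also be computed to assess for associations between certain variables. For example, higher neuroticism X higher negative emotions".

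On scoring, Section 9 says "Three scores can be derived from the MBSS questionnaire" (Monitoring, Blunting, and their difference). It does not choose one and gives no rule for who counts as a monitor or a blunter.

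**The concern.** Moderation means that the difference between arms varies with the trait. Estimating it needs both arms and an arm-by-trait term. Hypothesis 3 drops the control arm and the baseline. Hypothesis 4 lists monitoring and the traits as separate predictors with no product term. The Section 22 regressions contain neither trait, and the correlation example states neither arm nor time point. No hypothesis treats neuroticism as a moderator of symptoms.

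For neuroticism the protocol supplies the competing explanation itself: "neuroticism has been related to increased reports of physical symptoms in terms of both severity and frequency, even when comparing objectively healthy populations". An association inside the monitoring arm is therefore expected even if monitoring does nothing to these women in particular. If it is read as moderation, the trial could report that monitoring is worse for women high in neuroticism, or for monitors, when the same women report more symptoms in the control arm too.

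**Working it through.** **What each analysis estimates.** Write follow-up score = a + b·arm + c·trait + d·arm·trait, with arm 0 or 1. The objective is d.

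| Analysis in the plan | Trait quantity estimated |
|---|---|
| Hypothesis 3 (intervention arm only) | c + d |
| Correlation pooling two equal arms | based on c + d/2 |
| Hypothesis 4 (no product term) | c, with d assumed to be 0 |
| Group-by-time ANOVA; Section 22 regressions | no trait term |

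None isolates d. With d = 0 and c above 0, the first two still reject.

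**Sample sizes used.** Section 10 gives 52 completers (26 per arm) and 78 recruited (39 per arm). The 52 reproduces for a 1-df ANOVA effect if .40 is read as Cohen's f (power 0.807), and 52/(1 − 0.33) = 77.6, rounded up to 78. Reading .40 as d, as labelled, gives power 0.29 at 26 per arm; that is a separate issue. The calculation names no trait interaction.

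**Illustration with no moderation (d = 0).** The documents give no trait-symptom correlation r, so a range is assumed, equal in both arms. The median split, normal data and two-sided 5% tests are also assumed. For a median split, the mean difference is 2·√(2/π)·r = 1.596r and the within-group SD is √(1 − 2r²/π). At r = .3 this is 0.479/0.971 = 0.49 SD. A 13 v 13 t-test has power of about 23% at that difference; simulation gives 22%.

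Simulated rejection rates (20,000 runs; 6,000 for the interaction):

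| Analysis | r = 0 | .2 | .3 | .5 |
|---|---|---|---|---|
| Within-arm split, n = 26 | 5% | 12% | 22% | 55% |
| Within-arm split, n = 39 | 5% | 17% | 32% | 75% |
| Within-arm correlation, n = 26 | 5% | 16% | 33% | 77% |
| Pooled correlation, n = 52 | 5% | 30% | 59% | 97% |

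The interaction test, adjusted for baseline, rejects in 4–6% of trials across r = 0 to .5, at 26 or 39 per arm.

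**Precision of the corrected analysis, 26 per arm.** The model is follow-up = arm + baseline + trait + arm × trait. Slope differences of 0.2 to 0.5 SD per trait SD and the baseline–follow-up correlation ρ are assumed.

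| ρ | Power at 0.2 / 0.3 / 0.4 / 0.5 | 95% CI half-width |
|---|---|---|
| 0 | 10 / 19 / 28 / 39% | 0.59 |
| .5 | 13 / 22 / 36 / 49% | 0.51 |
| .7 | 16 / 29 / 48 / 65% | 0.42 |

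As a rough check, half-width ≈ t × √(1 − ρ²)/√(52 × 0.25). At ρ = 0 this is 2.01/3.61 = 0.56, slightly below the simulated 0.59 because the formula ignores chance variation in the trait's spread. With 39 per arm, power runs from 14–55% (ρ = 0) to 22–83% (ρ = .7).

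**The case against.** **The harm is conditional.** Hypothesis 3 is a valid test of what it literally states, and nothing in the plan says that it or the correlations will be read as moderation. The rates at r above 0 are power to detect a real, assumed association; they mislead only if they are interpreted as moderation. This stands as a limit on the claim. It does not close the gap, because nothing else in the plan addresses the objective.

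**Coping style has less support than neuroticism.** The protocol describes a symptom association without monitoring only for neuroticism. For coping style, the trait in hypothesis 3, r above 0 is purely an assumption, and at r = 0 the rate is the nominal 5%. This also stands.

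**The aim is exploratory, and the correlations are given only as examples.** True, but an exploratory estimate must still be of the intended quantity. The other interactions mentioned do not help: Section 22's is group by time, Section 10's power statement names no trait, and Section 10's covariate and subgroup plans concern health conditions and employment, living and relationship status.

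**The remedy is imprecise and brings several tests.** Two traits by three outcomes gives six interactions. If all were null and independent, the chance of at least one at 5% would be 1 − 0.95⁶ = 26%. That is a reason for estimates with intervals and an exploratory label, not for testing a different quantity.

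**Conclusion.** The concern holds. Moderation by coping style and neuroticism is a stated objective, and no arm-by-trait or arm-by-time-by-trait term appears anywhere in the plan. Followed as written, the plan answers a different question. This rests on the text alone and depends on none of the simulations.

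The size of the possible error does rest on assumptions. With no moderation and an assumed r of .2 to .5, the within-arm split at n = 26 would be significant in 12–55% of trials, against about 5% for the interaction. The primary group-by-time comparison is unaffected, so this is a change that should be made to a secondary objective, not a flaw in the main result.

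**What to change.** Restate hypothesis 3, and add to Section 22, an analysis that uses both arms:

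follow-up DRK score = arm + baseline DRK score + trait + arm × trait

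- Fit it for the DRK negative-emotion score and the DRK physical-symptom score. State which items form each score; hypothesis 3 already needs this.
- Fit it separately for one pre-specified continuous MBSS score (for example Monitoring minus Blunting) and for continuous neuroticism. This removes the need for a monitor/blunter cut-off.
- Use the same model for health anxiety, adjusted for its own baseline.
- Report every interaction estimate with its 95% CI and label it exploratory.
- State that within-arm contrasts and simple correlations will not be interpreted as moderation.

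An arm × time × trait term in the planned mixed ANOVA addresses the same question but is less precise: 40% against 50% power in one simulated case (26 per arm, slope difference 0.5, r = .3, ρ = .5).

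**Cost.** Wording only. Sections 8 and 9 already collect the traits, DRK and health anxiety in both arms at baseline, and the two outcomes again at follow-up. The downside to state is low precision: a null interaction from this trial will not show that moderation is absent.

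### The coping-style hypothesis compares monitors with blunters inside the intervention arm only, so it cannot show at which end of the coping scale, if either, daily symptom recording does harm

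*Combined protocol and SAP*

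**What the plan says.** Section 7 (Aims and objectives) names a risk for each coping style. For information-seekers, it says that "acquisition of health information can lead to increased health anxiety in individuals who exhibit monitoring coping preferences". For avoiders, it says that recording symptoms could be "taxing or even harmful should it challenge a dispositional tendency to avoid focusing on wellbeing". The coping measure is meant to show "whether symptom monitoring is more or less effective as an intervention for women, depending on their health information-seeking preferences", and the matching objective has no direction: "Assess whether personality and coping style moderate the impact of symptom monitoring on physical or emotional health outcomes during the menopause".

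Section 8 (Hypotheses, third bullet) turns this into a directed comparison within one arm: "Women in the intervention group who are monitors according to their scores on the blunting and monitoring scale will report higher negative emotions". In full, the prediction is that these women "will report higher negative emotions and physical symptoms than blunters at follow up", so blunters are the comparator and follow-up is the time point. The fourth hypothesis concerns health anxiety. Its list of predictors ends with "coping style, neuroticism, and symptom monitoring", gives no direction for coping style, and names no group by coping-style term.

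Section 9 (Miller Behavioural Style Scale) lists three possible scores: total Monitoring, total Blunting, and "the total difference score- Monitoring minus Blunting". It does not choose one and gives no cut-off for calling a woman a monitor or a blunter.

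Section 22 (Data analysis) plans a group by time ANOVA, multiple and logistic regressions, and correlations. Coping style is not named in the ANOVA or the regressions, and no moderation model is described.

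**The concern.** The rationale asks two questions: does daily recording harm women who seek health information, and does it harm women who avoid it? Each needs a comparison with women of the same coping style who did not record. The third hypothesis compares the two styles with each other among women who all recorded. That answers a different question, namely which style ends up with the higher score.

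At stake is a stated aim of the trial, to learn for whom the intervention may be taxing or harmful. If the plan is followed as written, harm common to both styles drops out of the coping-style comparison. Harm confined to avoiders has no hypothesis of its own and shows up only as a reversal of the third one. Because follow-up scores are compared rather than changes, a difference between the styles that was there at baseline is also counted as if the intervention had caused it.

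**Working it through.** **Plan's own figure.** The plan gives no sample-size figure for the third hypothesis. Its only figure (Section 10, Power analysis) is 52 in total, 26 per group, raised to 78, or 39 per group. With 0.40 read as Cohen's f, two groups and alpha 0.05, 52 gives power 0.8075 and 51 gives 0.7996, so 52 is reproduced on that reading. For attrition, 52 / (1 - 0.33) = 77.6, rounded up to 78. These figures are used below only to set group sizes.

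**Formula.** Let hM and hB be the harm caused by recording in monitors and blunters, in SD units, and let δ be any monitor-blunter difference that would exist without the intervention.

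- Third-hypothesis contrast = hM - hB + δ
- Shift in the intervention-arm mean, if the arm splits evenly = (hM + hB) / 2

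**Assumptions, not taken from the documents.** The harms are illustrative and δ = 0 in the table. The intervention arm splits evenly: 13 v 13 of 26 completers, or in brackets 19 v 19 of 38 of the 39 randomised. Tests are two-sided at 0.05. The last column is a simple comparison of arms, standing in for the group by time test.

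| hM | hB | Contrast | Rejection rate, 13 v 13 (19 v 19) | Arm-mean shift | Arm comparison, 26 v 26 (38 v 38) |
|---|---|---|---|---|---|
| 0.8 | 0.8 | 0 | 0.05 (0.05) | 0.8 | 0.81 (0.93) |
| 0.8 | 0.4 | +0.4 | 0.17 (0.22) | 0.6 | 0.56 (0.73) |
| 0.4 | 0.8 | -0.4 | 0.17 (0.22), reversed | 0.6 | 0.56 (0.73) |
| 0 | 0.8 | -0.8 | 0.50 (0.67), reversed | 0.4 | 0.29 (0.41) |
| 0.8 | 0 | +0.8 | 0.50 (0.67) | 0.4 | 0.29 (0.41) |

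Three things follow.

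1. The shared part of the harm drops out. The contrast is zero only if the two harms are equal and δ = 0. Otherwise it is their difference plus δ, which does not give the size of either.
2. Harm to blunters alone reverses the sign of the predicted contrast.
3. With no harm at all and δ = 0.8, the contrast is 0 - 0 + 0.8 = +0.8, the same as in the last row. A pre-existing difference can therefore support the hypothesis without any effect of the intervention.

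**Checking the alternative.** Take a model with arm, total Monitoring (M), total Blunting (B), arm by M and arm by B, with scores in SD units, and read off the intervention-versus-control effect at +1 SD of each score with the other score at its mean.

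- *Avoiders only, 0.4 SD worsening per SD of B.* The effect at high Blunting is 0.4 × 1 = 0.4 SD, and at high Monitoring it is 0.4 × 0 = 0. Simulation returns about 0.4 and 0.
- *Both ends, 0.8 SD worsening per SD of |M - B|.* By symmetry both interaction slopes average zero. The joint test of the two interactions rejects about 6 to 7% of the time at 26 per arm, close to alpha. The estimated effect at each end is about 0.8 × √(2/π) = 0.8 × 0.798 = 0.64 SD, and simulation returns about 0.6. This is the average harm carried level across the scale. It shows harm at each end but cannot show whether the middle is spared.

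**Precision.** For 13 v 13 within one coping group, the standard error is √(2/13) = 0.392 SD and the 95% half-width is 2.064 × 0.392 = 0.81 SD. For 19 v 19 it is 2.028 × 0.324 = 0.66 SD. A true 0.8 SD harm in one group would be detected with power 0.50 (0.67).

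**The case against.** The case for leaving the plan alone has real substance.

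- **Shared harm is still visible.** It would move the intervention-arm mean and so the group by time result. This stands. A reader might infer that harm at both ends vanishes from the trial, but the documents do not support that. The coping-style contrast loses it and the main comparison does not. What the main comparison cannot do is say who is harmed. It is also expected to show average benefit, which could hide harm in a subgroup.
- **A directed expectation is not a one-sided test.** The only sidedness stated is two-tailed, in the power analysis, and the objective is undirected. A reversed result could be detected and reported. This stands. A reader might infer that harm to avoiders would be dismissed as a failed hypothesis, but the documents do not say so.
- **The risk named for information-seekers is health anxiety, which has its own hypothesis.** This stands in part. Section 9 also says that any effect on health anxiety will be examined against coping preferences. But neither the fourth hypothesis nor Section 22 names a group by coping-style term. The risk to avoiders is not limited to anxiety.
- **The difference score is not chosen.** Correct. A reader might infer that the plan commits to Monitoring minus Blunting. Section 9 leaves all three scores open, so the separate totals remain available.
- **Separate terms do not by themselves find harm at both ends.** Correct, as the joint-test result shows. A reader might infer that adding two interactions recovers both harms, but when both ends are harmed alike the interactions show nothing. Only the comparison with control at each end is informative.

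**Conclusion.** The point holds in a limited form. The third hypothesis does not answer the question set in Section 7, and nothing in Section 22 fills the gap. As planned, the coping-style analysis yields harm in monitors minus harm in blunters plus any pre-existing difference, and it isolates harm at neither end. Under the assumed harms, the contrast is 0 for equal harm of 0.8 SD, +0.4 SD for harms of 0.8 and 0.4, and -0.8 SD for harm of 0.8 SD to blunters only. These sizes are illustrations and rest on an even split and no pre-existing difference. The structure of the contrast does not depend on them.

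This does not mean that the trial is blind to harm, or that a better model would settle the matter. With 26 to 39 women per arm, any statement about who is harmed will be imprecise. The gain from the change is that the estimate addresses the stated objective and has a control reference.

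**What to change.** 1. Replace the third hypothesis with a two-sided moderation statement: the intervention-versus-control effect on negative emotions and on physical symptoms varies with the total Monitoring score and with the total Blunting score.
2. Add the matching model to Section 22. Enter the two totals from Section 9 as separate continuous terms, each with its own arm interaction, and do not use a monitor/blunter label or the difference score.
3. Report the intervention-versus-control effect with its confidence interval at high Monitoring and at high Blunting, with the values that count as high fixed in advance.
4. Base the conclusion about who is harmed on those control-referenced effects and not on the joint interaction test, which has essentially no power beyond alpha when both ends are harmed alike.
5. Label the analysis exploratory.

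The cost is a reworded hypothesis and one added secondary model with a few more parameters. No new data are needed, since both arms complete the coping scale at baseline and the symptom form at baseline and follow-up. The downside is low precision, with a 95% half-width of roughly 0.7 to 0.8 SD for an effect within one coping group.

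### Hypothesis 4 models follow-up health anxiety without the baseline score, so its trait terms can reflect differences that existed before the study, and the monitoring term loses precision

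*Combined protocol and SAP*

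**What the plan says.** Section 8 (Hypotheses) gives the full predictor list: "Greater Health anxiety at follow up will be predicted by symptom changes, demographics (living alone, employment, and marital status), coping style, neuroticism", and symptom monitoring. The outcome is a level at follow-up. Symptoms enter as change, but health anxiety does not.

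Section 9 (Health anxiety subscale) says the scale is measured twice ("HOS; to be assessed at baseline and follow-up") and gives the purpose: "health anxiety will be assessed to explore whether symptom monitoring influences it, and whether this effect is related to neuroticism or coping preferences". It describes high scorers in lasting terms: "People who endorse these items are those who experience chronic anxiety as a result of thinking about their physical health".

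Section 7 says of neuroticism that "it has empirically been associated with increased reports of health anxiety". It adds that "coping style and neuroticism have both been associated with increased health anxiety", in that case after obtaining health information. Section 8 says neither trait is expected to alter over the two weeks, so both are measured at baseline only.

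Section 22 has no model with health anxiety as the outcome. The mixed ANOVA is described for symptoms. Health anxiety appears only as a predictor, of group membership and of help-seeking: "Multiple regressions will explore whether help-seeking intentions as continuous variables as predicted by symptom monitoring group (dummy coded", followed by further predictors. That list has no baseline help-seeking score and gives no time point for the outcome. Nowhere do the documents say that baseline health anxiety will be adjusted for.

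**The concern.** The stated question is whether monitoring alters health anxiety, and for whom. The listed model explains who is anxious on day 15. If neuroticism is stable, already linked to health anxiety, and health anxiety is itself long-lasting, neuroticism will tend to predict day-15 anxiety even when nothing happens during the study. A significant trait coefficient would then say little about the two weeks.

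This matters because section 7 wants to know for whom monitoring could be unhelpful or harmful, and the trait findings will be read in that light. There is a second cost. The baseline score is probably the strongest available predictor of the follow-up score, and leaving it out makes the estimate of monitoring's effect on anxiety less precise than the collected data allow.

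**Working it through.** **Plan's own figures.** None is given for hypothesis 4. The evaluable total of 52 in section 10 reproduces (power .807) only if the effect of .40 is Cohen's f, although the text labels it d. With 33% attrition, 52 / 0.67 = 77.6, which gives 78. I use n = 52.

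**Inputs.** From the documents: the seven predictors (group, neuroticism, coping, symptom change, three demographics) and a two-sided alpha of .05. Assumed, because the documents give no values: neuroticism–baseline anxiety correlation r and baseline to day-15 correlation s, paired as .3/.6, .4/.7 and .5/.8. Coping, symptom change and demographics are taken as unrelated to the outcome. There is no effect of monitoring or of participation.

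**Method.** Seven predictors and an intercept leave 52 − 8 = 44 degrees of freedom, or 43 with baseline added. A predictor with partial correlation ρ has noncentrality ρ/√(1 − ρ²) × √df, and power follows from the noncentral t distribution.

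**Case A: neuroticism acts only through the observed baseline score.** Without baseline, ρ = r × s. With baseline, ρ = 0.

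**Case B: anxiety is a stable trait measured with error.** Without baseline, ρ = r. With baseline, ρ = r(1 − s)/√[(1 − r²)(1 − s²)]. At .4/.7 this is .12/√(.84 × .51) = .183.

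Percentage of trials with neuroticism significant at n = 52, by formula:

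| r / s | A, no baseline | A, with baseline | B, no baseline | B, with baseline |
|---|---|---|---|---|
| .3 / .6 | 22 | 5 | 53 | 18 |
| .4 / .7 | 47 | 5 | 81 | 22 |
| .5 / .8 | 81 | 5 | 96 | 24 |

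Simulations of the full regression agree: about 21–80% and 5% in case A, 54–95% and 15–26% in case B. These use paired values. Crossing the ranges widens the residual in case B: at .5/.6, ρ = .20/√(.75 × .64) = .289, and neuroticism is still significant in about half of trials after adjustment. With correlations .3 to .5 and test–retest .70 to .85, simulation gave 10–37% remaining at n = 52 and 12–55% at n = 78.

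**Change scores.** In case B, analysing follow-up minus baseline brought neuroticism to 4–6%. In case A it gave 15–19%. Change scores are therefore not a general cure.

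**Monitoring term.** Group is randomised. Its term was significant in about 4–5% of null trials with or without baseline. For precision at .4/.7 in case A, ignoring the small allowance for other covariates:
- without baseline, (2/√52) × √(1 − .28²) = .277 × .960 = .27 SD
- with baseline, .277 × √(1 − .49) = .277 × .714 = .20 SD

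With all covariates fitted, simulation gives .28 and .21. If monitoring raised anxiety by 0.4 SD (r = .4, test–retest .70 to .85), power for the group term at n = 52 rises from 28–32% to 47–70% with baseline adjustment.

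**The case against.** **The hypothesis as worded may simply be true.** It says follow-up anxiety will be predicted by neuroticism. If the two correlate, a significant coefficient is a correct detection. This stands: the percentages above are not error rates for that sentence. They become misleading only when the coefficient is read as change during the study or as an effect of monitoring.

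**Stable differences cannot confirm the monitoring part.** A reader might infer that the omission lets the whole hypothesis succeed without any effect. The documents do not support that. Monitoring is randomised and its term keeps its 5% error rate. No rule says that significant trait terms alone count as confirmation.

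**A neuroticism main effect cannot show risk from monitoring.** A reader might also infer that the trial would report neurotic women as harmed by monitoring. The coefficient is pooled over both arms, so it cannot show this, adjusted or not. That question needs a group-by-trait term, which hypothesis 4 does not list.

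**Adjustment is not a complete cure.** This stands. The fall to about 5% holds only in case A. When baseline is measured with error, residual association remains.

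**The list is a hypothesis, not a model.** Section 22 has no model for it, which is a separate gap. A model written from the stated list would still carry this fault.

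**Help-seeking.** Section 22 gives no time point for that outcome, so the parallel point is only conditional.

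**Conclusion.** The point holds in limited form. The predictor list omits a baseline score that is collected from every woman, and nothing elsewhere in the documents repairs this. Trait terms can therefore be significant because of differences that existed before the study: about 21–80% of null trials in case A and 54–95% in case B at n = 52. Baseline adjustment brings these to about 5% and about 15–26%. All four ranges rest on assumed correlations, and case B is wider if those are crossed.

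The argument is clearest for neuroticism. For coping style the cited association follows the obtaining of health information, and the simulations gave it no effect. For monitoring, the loss is of precision only, about .28 against .21 SD. That coefficient also conditions on symptom change, which arises after randomisation and which monitoring is meant to alter, so it is not the total effect of monitoring on anxiety. The hypothesis is secondary and exploratory. The change is worth making because it is cheap and bears on possible harm.

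**What to change.** - Write the hypothesis 4 model with baseline Health Anxiety as a covariate.
- State that main effects of neuroticism, coping and demographics will not be read as effects of monitoring or of taking part, because some association from before the study remains after adjustment.
- To answer the section 9 question, add group-by-neuroticism and group-by-coping terms to the baseline-adjusted model, and label them exploratory at this sample size.
- Estimate the total effect of monitoring on health anxiety from a baseline-adjusted model without the symptom-change term.
- State the time point of help-seeking in section 22. If it is follow-up, include the baseline help-seeking score as well.

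Cost: one degree of freedom per added term and a few lines of text. No new data and no extra burden on participants.
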